9.6.1 Expected AEs from Temozolomide

See product insert (section 14.4). Adverse events and toxicities will be managed per institutional and accepted standard of care practices.

Table 9 Evaluating Adverse Events

An investigator who is a qualified physician, will evaluate all adverse events as to:

V4.0 CTCAE Grading	Grade 1	Mild; asymptomatic or mild symptoms; clinical or diagnostic observations only; intervention not indicated.
	Grade 2	Moderate; minimal, local or noninvasive intervention indicated; limiting age-appropriate instrumental ADL.
	Grade 3	Severe or medically significant but not immediately life-threatening; hospitalization or prolongation of hospitalization indicated; disabling; limiting self-care ADL.
	Grade 4	Life threatening consequences; urgent intervention indicated.
	Grade 5	Death related to AE
Seriousness	A serious adverse event is any adverse event occurring at any dose or during any use of Merck product that:	
	† Results in death ; or	
	† Is life threatening ; or places the subject, in the view of the investigator, at immediate risk of death from the event as it occurred (Note: This does not include an adverse event that, had it occurred in a more severe form, might have caused death.); or	
	† Results in a persistent or significant disability/incapacity (substantial disruption of one's ability to conduct normal life functions); or	
	† Results in or prolongs an existing inpatient hospitalization (hospitalization is defined as an inpatient admission, regardless of length of stay, even if the hospitalization is a precautionary measure for continued observation. (Note: Hospitalization [including hospitalization for an elective procedure] for a preexisting condition which has not worsened does not constitute a serious adverse event.); or	
	† Is a congenital anomaly/birth defect (in offspring of subject taking the product regardless of time to diagnosis); or	
	Is a new cancer ; (that is not a condition of the study) or	
	Is an overdose (whether accidental or intentional). Any adverse event associated with an overdose is considered a serious adverse event. An overdose that is not associated with an adverse event is considered a non-serious event of clinical interest and must be reported within 24 hours.	
	Other important medical events that may not result in death, not be life threatening, or not require hospitalization may be considered a serious adverse event when, based upon appropriate medical judgment, the event may jeopardize the subject and may require medical or surgical intervention to prevent one of the outcomes listed previously (designated above by a †).	
Duration	Record the start and stop dates of the adverse event. If less than 1 day, indicate the appropriate length of time and units	
Action taken	Did the adverse event cause the Merck product to be discontinued?	
Relationship to test drug	Did the Merck product cause the adverse event? The determination of the likelihood that the Merck product caused the adverse event will be provided by an investigator who is a qualified physician. The investigator's signed/dated initials on the source document or worksheet that supports the causality noted on the AE form, ensures that a medically qualified assessment of causality was done. This initialed document must be retained for the required regulatory time frame. The criteria below are intended as reference guidelines to assist the investigator in assessing the likelihood of a relationship between the test drug and the adverse event based upon the available information. The following components are to be used to assess the relationship between the Merck product and the AE ; the greater the correlation with the components and their respective elements (in number and/or intensity), the more likely the Merck product caused the adverse event (AE):	
	Exposure	Is there evidence that the subject was actually exposed to the Merck product such as: reliable history, acceptable compliance assessment (pill count, diary, etc.), expected pharmacologic effect, or measurement of drug/metabolite in bodily specimen?
	Time Course	Did the AE follow in a reasonable temporal sequence from administration of the Merck product? Is the time of onset of the AE compatible with a drug-induced effect (applies to trials with investigational medicinal product)?
	Likely Cause	Is the AE not reasonably explained by another etiology such as underlying disease, other drug(s)/vaccine(s), or other host or environmental factors

Relationship to Merck product (continued)	The following components are to be used to assess the relationship between the test drug and the AE: (continued)	
	Dechallenge	
Was the Merck product discontinued or dose/exposure/frequency reduced?
 
If yes, did the AE resolve or improve?
 
If yes, this is a positive dechallenge. If no, this is a negative dechallenge.
 
(Note: This criterion is not applicable if: (1) the AE resulted in death or permanent disability; (2) the AE resolved/improved despite continuation of the Merck product; or (3) the trial is a single-dose drug trial; or (4) Merck product(s) is/are only used one time.)

	Rechallenge	
Was the subject re-exposed to the Merck product in this study?
 
If yes, did the AE recur or worsen?
 
If yes, this is a positive rechallenge. If no, this is a negative rechallenge.
 
(Note: This criterion is not applicable if: (1) the initial AE resulted in death or permanent disability, or (2) the trial is a single-dose drug trial); or (3) Merck product(s) is/are used only one time).
 
NOTE: IF A RECHALLENGE IS PLANNED FOR AN ADVERSE EVENT WHICH WAS SERIOUS AND WHICH MAY HAVE BEEN CAUSED BY THE MERCK PRODUCT, OR IF REEXPOSURE TO THE MERCK PRODUCT POSES ADDITIONAL POTENTIAL SIGNIFICANT RISK TO THE SUBJECT, THEN THE RECHALLENGE MUST BE APPROVED IN ADVANCE BY THE U.S. CLINICAL MONITOR AS PER DOSE MODIFICATION GUIDELINES IN THE PROTOCOL.

	Consistency with Trial Treatment Profile	Is the clinical/pathological presentation of the AE consistent with previous knowledge regarding the Merck product or drug class pharmacology or toxicology?
The assessment of relationship will be reported on the case report forms /worksheets by an investigator who is a qualified physician according to his/her best clinical judgment, including consideration of the above elements.		
Record one of the following		Use the following scale of criteria as guidance (not all criteria must be present to be indicative of a Merck product relationship).
Yes, there is a reasonable possibility of Merck product relationship.		There is evidence of exposure to the Merck product. The temporal sequence of the AE onset relative to the administration of the Merck product is reasonable. The AE is more likely explained by the Merck product than by another cause.
No, there is not a reasonable possibility Merck product relationship		Subject did not receive the Merck product OR temporal sequence of the AE onset relative to administration of the Merck product is not reasonable OR there is another obvious cause of the AE. (Also entered for a subject with overdose without an associated AE.)

9.6.2 Definition of an Overdose for This Protocol and Reporting of Overdose to the Sponsor and to Merck

For purposes of this trial, an overdose of pembrolizumab will be defined as any dose of 1,000 mg or greater (≥ 5 times the indicated dose). No specific information is available on the treatment of overdose of pembrolizumab. Appropriate supportive treatment should be provided if clinically indicated. In the event of overdose, the subject should be observed closely for signs of toxicity. Appropriate supportive treatment should be provided if clinically indicated.

If an adverse event(s) is associated with (“results from”) the overdose of a Merck product, the adverse event(s) is reported as a serious adverse event, even if no other seriousness criteria are met.

If a dose of Merck’s product meeting the protocol definition of overdose is taken without any associated clinical symptoms or abnormal laboratory results, the overdose is reported as a non-serious Event of Clinical Interest (ECI), using the terminology “accidental or intentional overdose without adverse effect.”

All reports of overdose with and without an adverse event must be reported within 24 hours to the Sponsor and within 2 working days hours to Merck Global Safety (Attn: Worldwide Product Safety; [contact]).

9.6.3 Reporting of Pregnancy and Lactation to the Sponsor and to Merck

Although pregnancy and lactation are not considered adverse events, it is the responsibility of investigators or their designees to report any pregnancy or lactation in a subject (spontaneously reported to them), including the pregnancy of a male subject's female partner that occurs during the trial or within 120 days of completing the trial completing the trial, or 30 days following cessation of treatment if the subject initiates new anticancer therapy, whichever is earlier. All subjects and female partners of male subjects who become pregnant must be followed to the completion/termination of the pregnancy. Pregnancy outcomes of spontaneous abortion, missed abortion, benign hydatidiform mole, blighted ovum, fetal death, intrauterine death, miscarriage and stillbirth must be reported as serious events (Important Medical Events). If the pregnancy continues to term, the outcome (health of infant) must also be reported.

Such events must be reported within 24 hours to the Sponsor and within 2 working days to Merck Global Safety (Attn: Worldwide Product Safety; [contact]).

9.6.4 Immediate Reporting of Adverse Events to the Sponsor and to Merck

9.6.4.1 Serious Adverse Events

A serious adverse event is any adverse event occurring at any dose or during any use of Merck’s product that:

- Results in death;
- Is life threatening;
- Results in persistent or significant disability/incapacity;
- Results in or prolongs an existing inpatient hospitalization;
- Is a congenital anomaly/birth defect;

- Is a new cancer (that is not a condition of the study);
- Is associated with an overdose;
- Is another important medical event

Refer to Table 8 for additional details regarding each of the above criteria.

Any serious adverse event, or follow up to a serious adverse event, including death due to any cause other than progression of the cancer under study that occurs to any subject from the time the consent is signed through 90 days following cessation of treatment, or the initiation of new anti-cancer therapy, whichever is earlier, whether or not related to Merck product, must be reported within 24 hours to the Sponsor and within 2 working days to Merck Global Safety.

Non-serious Events of Clinical Interest will be forwarded to Merck Global Safety and will be handled in the same manner as SAEs.

Additionally, any serious adverse event, considered by an investigator who is a qualified physician to be related to Merck product that is brought to the attention of the investigator at any time outside of the time period specified in the previous paragraph also must be reported immediately to the Sponsor and to Merck.

SAE reports and any other relevant safety information are to be forwarded to the Merck Global Safety [contact]

A copy of all 15 Day Reports and Annual Progress Reports is submitted as required by FDA, European Union (EU), Pharmaceutical and Medical Devices agency (PMDA) or other local regulators. Investigators will cross reference this submission according to local regulations to the Merck Investigational Compound Number (IND, CSA, etc.) at the time of submission. Additionally investigators will submit a copy of these reports to Merck & Co., Inc. (Attn: Worldwide Product Safety; [contact]) at the time of submission to FDA.

All subjects with serious adverse events must be followed up for outcome.

9.6.4.2 Events of Clinical Interest

Selected non-serious and serious adverse events are also known as Events of Clinical Interest (ECI) and must be recorded as such on the Adverse Event case report forms/worksheets and reported within 24 hours to the Sponsor and within 2 working days to Merck Global Safety (Attn: Worldwide Product Safety; [contact]).

Events of clinical interest for this trial include:

1. an overdose of Merck product, as defined in Section 9.6.1 - Definition of an Overdose for This Protocol and Reporting of Overdose to the Sponsor, that is not associated with clinical symptoms or abnormal laboratory results.

2. an elevated AST or ALT lab value that is greater than or equal to 3X the upper limit of normal and an elevated total bilirubin lab value that is greater than or equal to 2X the upper limit of normal and, at the same time, an alkaline phosphatase lab value that is less than 2X the upper limit of normal, as determined by way of protocol-specified laboratory testing or unscheduled laboratory testing.*

*Note: These criteria are based upon available regulatory guidance documents. The purpose of the criteria is to specify a threshold of abnormal hepatic tests that may require an additional evaluation for an underlying etiology. The trial site guidance for assessment and follow up of these criteria can be found in the Investigator Trial File Binder (or equivalent).

9.6.5 Evaluating Adverse Events

An investigator who is a qualified physician will evaluate all adverse events according to the NCI Common Terminology for Adverse Events (CTCAE), version 4.0. Any adverse event which changes CTCAE grade over the course of a given episode will have each change of grade recorded on the adverse event case report forms/worksheets.

All adverse events regardless of CTCAE grade must also be evaluated for seriousness.

10.0 STATISTICAL ANALYSIS PLAN

Given the exploratory nature of this study, the statistical analyses will be descriptive in nature. For the primary and secondary objectives, sensitivity, specificity, rate of adverse event and distribution of best responses will be analyzed using proportions and exact 95% confidence intervals. Progression free survival and overall survival will be assessed using the Kaplan-Meier product limit estimates. Outcomes in the exploratory objectives will be summarized using descriptive statistics as appropriate; and associations between immunological parameters, PDL-1 expression, clinical responses, radiological responses and other variables will be explored using two sample tests or correlation measures, as appropriate.

Power and sample size calculation for Arm 1

The accrual to arm 1 is stopped with 2 patients. These 2 patients will be described separately and no further analysis will be done.

Power and sample size calculation for Arm 2

For arm 2, we will enroll 43 GBM patients. Here we roughly estimate the precision of sensitivity and specificity in the primary objective based on these 43 patients.

In subjects with GBM, we anticipate to have only one lesion/subject. We assume that all subjects will eventually have disease progression and due to dropout and inoperable cases, a total of $n = 32$ subjects will undergo surgery to provide histopathological data on disease progression. Further, we assume that 40% of the $n = 43$ subjects will develop pseudo-progression and be observed based on follow-up scan.

For sensitivity, further assume that out of the $n = 32$ subjects who will undergo surgery, 26 subjects will have true progression based on pathology (gold standard). Then based on $n = 26$,

if we observe 22 subjects (lesions) for whom the true progression is correctly identified by Ferumoxytol MRI, then the sensitivity will be 85% with a 95% CI between 65% and 96% (Table XX).

Number of subjects (lesions) with true progression	Number of subjects (lesions) whose true progression was detected by Ferumoxytol MRI	Sensitivity	Exact 95% CI of Sensitivity
26	26	100%	87% to 100%
26	24	92%	75% to 99.1%
26	22	85%	65% to 96%
26	20	77%	56% to 91%
26	18	69%	48% to 86%
26	16	62%	41% to 80%

Table 12: Estimated sensitivity and 95% CI based on 26 subjects (lesions).

For specificity, it will be calculated based on patients with pseudo-progression determined by either surgical results or follow-up scan. We assume that 40% of the subjects (n = 17) will develop pseudo-progression, then if we observe 15 subjects (lesions) for whom the pseudo-progression status is correctly identified by ferumoxytol MRI, the specificity will be 88% with a 95% CI between 64% and 99% (Table 13).

Number of lesions with pseudo-progression	Number of Lesions with pseudo-progression detected by Ferumoxytol MRI	Specificity	Exact 95% CI of Specificity
17	17	100%	80% to 100%
17	15	88%	64% to 99%
17	13	76%	50% to 93%
17	11	65%	38% to 86%

Table 13: Estimated specificity and 95% CI based on 17 patients.

Statistical Analysis

For arm 2, sensitivity, specificity, rate of adverse events (safety and tolerability) and the distribution of best responses will be analyzed using proportions and exact 95% confidence intervals. In the primary analysis of sensitivity and specificity, the cutoff for rCBV will be specified as 1.75 (<1.75 is pseudoprogression and ≥ 1.75 is progression). Analysis of sensitivity will be based on patients with surgical results, and specificity analysis will be based on patients with pseudo-progression determined based on surgical results or follow-up clinical scan, as detailed in the power and sample size calculation section. In secondary analysis, we will try other cutoff points for rCBV, and include all patients that will be confirmed with true progression through surgery or follow up imaging. Progression free survival and overall survival will be assessed using the Kaplan-Meier product limit estimates for all patients, taking censoring into account. For exploratory objectives, continuous variables will be summarized

using mean and standard deviation, or median and range based on the distribution of data. The categorical variables will be summarized using frequencies and proportions, with exact 95% CI as appropriate.

Exploratory objectives 1 to 3 will be analyzed using patients from arm 2. Immune responses will be determined by the volume, pattern and intensity of delayed (24hr) ferumoxytol uptake and compared between patients who develop true vs. pseudoprogression and provided data using Wilcoxon Rank Sum test (volume and intensity) or Fisher's exact test (pattern). Systemic immune responses will be measured by immunological parameters (CD3, CD4, CD8, CD19, CD25, CD27, CD45, CD56, CD45R0, CD45RA, titers of IgD, $T\gamma\delta$ and $T\alpha\beta$) and correlated with clinical responses (complete response, disease progression, pseudoprogression etc.) using Wilcoxon Rank Sum test, and with radiological response (size of tumor) using Pearson's correlation coefficient or Spearman's correlation coefficient.

For exploratory objective 3, among the 43 patients, 8 to 10 patients are expected to have data on PD-1 receptor expression (Yes vs. No, where Yes is defined as $\geq 1\%$ PDL-1 expression and No as $< 1\%$ based on FDA recommendations <https://www.keytruda.com/static/pdf/keytruda-pd-l1-expression-testing-guide.pdf>) and immune cells (T cells, CD4+, CD8+, macrophages, M1, M2 etc) before initiation of Pembrolizumab and at the time of progression. If data allow, we will compare the PD-1 receptor expression and immune cells data before initiation of Pembrolizumab and at the time of progression using exact McNemar's test or Wilcoxon signed test to accommodate the paired nature of the data, and use univariate logistic or Cox regression models to correlate PD-L1 expression with response rates and survival. Lastly, in metastatic patients with measurable systemic lesions, vascular volume fraction (VVF), vessel size index (VSI) and vessel density index (VDI) will be measured and compared between patients with true vs. pseudoprogression, if data allow.

In summary, all these proposed analyses will be conducted on the exploratory basis. A two-sample t-test may be used if the data show adequate normality. We will only provide descriptive statistics if the comparison mentioned above won't yield clinical meaningful results. The purpose of these exploratory analyses is to see whether some preliminary signals in the data could be detected.

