progression or toxicity. Ferumoxytol MRI (FeMRI) will be performed in the same day and sitting as the clinical MRI at baseline and 4 weeks after the last day of radiation timepoints. FeMRI may be performed independently (on a different day or different MRI setting) of the clinical MRI if there is suspected radiographic progression or to confirm radiographic progression. If there is suspected progression, subjects undergo a ferumoxytol steady state MRI and continue on pembrolizumab for one more cycle. The decision regarding continuation of pembrolizumab will be made by the principle investigator based on clinical findings that include (1) stable ECOG performance status with no more than 8mg of dexamethasone (or equivalent) a day; (2) absence of new or worsening symptoms not managed with steroids; and (3) absence of progressive tumor at critical anatomical sites (e.g., spinal cord compression) requiring urgent alternative medical intervention. Follow up clinical standard of care and ferumoxytol MRIs will be repeated to confirm persistent radiographic progression in 4 weeks. During this 4 week follow up period, subjects will be followed with a clinical exam weekly to monitor for clinical stability. If the 4 week follow up scan confirms progression (as defined in section 8.1), then pembrolizumab is discontinued and subject is evaluated for clinical indication of standard of care surgery or biopsy. Surgery or biopsy is performed only if 1) the lesion is deemed easily accessible 2) surgery is not expected to worsen neurological outcomes and 3) it is in the best clinical interest of the subject. The decision regarding surgery will be consensus based and when possible, will be made after each individual case has been presented at the OHSU multi-disciplinary brain tumor board. If histopathology confirms pseudoprogression or is inconclusive, the subject will continue on pembrolizumab every 3 weeks until further radiographic progression is suspected. If histopathology confirms progression, the subject will be removed from the study. Subjects with evidence of new lesions distant from the primary lesion/s (not present at entry to the study) in the CNS or systemically that fulfil criteria for progression by immune related response criteria (irRC)[1] will be taken off study drug, but will be followed with serial clinical standard of care MRI.

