When there is radiologic progression after radiation, current standard of care includes repeat craniotomy to confirm true vs pseudoprogression. Biopsy tissue obtained from surgery at persistent radiographic progression will be evaluated by the pathologists at OHSU. The pathologist will determine if the tissue is consistent with progression or pseudoprogression, where progression is defined as presence of viable metastatic carcinoma in the biopsy tissue and absence of tumor cell is assumed to reflect pseudoprogression. If histopathology confirms pseudoprogression the subject will continue on pembrolizumab every 3 weeks until further radiographic progression is suspected. If histopathology confirms progression, the subject will be removed from the study, followed clinically with serial clinical standard of care MRIs every 3 months for up to a year and then every 6 months until death or lost to follow-up.

Standard of care surgery or biopsy is performed only if 1) the lesion is deemed easily accessible 2) surgery is not expected to worsen neurological outcomes and 3) it is in the best clinical interest of the patient. The decision regarding surgery will be consensus based and when possible, will be made after each individual case has been presented at the OHSU multidisciplinary brain tumor board. If a subject is not a surgical candidate, or is unwilling to undergo surgery, they will be taken off study. They will, however, be eligible for continuation of pembrolizumab, at the physician's discretion, at the same dose and frequency, if clinical benefit is noted. They will be followed clinically with serial clinical standard of care MRI scans as described in section 7.11.

In subjects where the lesion remains unchanged or regresses in volume at 4 weeks (± 5 days) after the date of suspected radiographic progression, pembrolizumab will be continued until further persistent radiographic progression is confirmed.

All subjects will be followed with clinical examination and clinical standard of care MRI scans until death or lost to follow up. Subjects will be treated for up to 2 years, toxicity, or progression whichever comes first. Dose reductions/discontinuations for pembrolizumab will be as per Merck guidelines.

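### Primary sensitivity is estimated only in operated patients, about a quarter are expected to go unverified, and no correction or bounds for this are planned

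*Combined protocol and SAP*

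**What the plan says.** Section 10.0 (Statistical Analysis) fixes the rCBV cut-off at 1.75 and restricts the primary sensitivity: "Analysis of sensitivity will be based on patients with surgical results". Specificity has a wider reference standard, accepting pseudoprogression shown by surgery or by follow-up scan. A secondary analysis tries other cut-offs and will "include all patients that will be confirmed with true progression through surgery or follow up imaging".

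The planning figures are in the same section (Power and sample size calculation for Arm 2): "For arm 2, we will enroll 43 GBM patients"; "We assume that all subjects will eventually have disease progression"; and, "due to dropout and inoperable cases", 32 will have surgery. Of those 32, 26 are expected to show true progression on pathology. The worked case is 22 of 26 detected, 85% with an exact 95% interval of 65% to 96%. Separately, 17 subjects (40%) are expected to develop pseudoprogression.

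On sequence, Sections 2.0, 6.0 and 7.4 place a ferumoxytol MRI at suspected progression and another about 4 weeks later, with evaluation for surgery after that. Section 7.4 says: "Standard of care surgery or biopsy is performed only if 1) the lesion is deemed easily accessible"; the other two conditions are neurological risk and the subject's best clinical interest. Section 2.0 adds: "The decision regarding surgery will be consensus based". Section 8.1 also provides for patients who refuse biopsy or for whom it is not thought clinically necessary. The only masking described is that of the two radiologists (Sections 7.6 and 8.2.1), to map type and subject information.

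**The concern.** The index test is read before the reference standard is chosen, and the primary sensitivity counts only those who receive that standard. If the chance of surgery among true progressors differs between high and low rCBV, the operated patients are not a fair sample of progressors for judging rCBV, and the sensitivity shifts.

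Such a link is plausible. Section 4.3.1 presents rCBV on ferumoxytol imaging as very helpful for telling pseudoprogression from true progression, and Section 4.0 describes a patient classed as pseudoprogression on low blood volume. A team with that view and access to the scan might be less inclined to operate when rCBV is low. Those patients would be the missed progressions, and they would leave the denominator.

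The study tests no hypothesis, so the estimate and its interval are the whole primary result, and the data are meant to power a larger study (Section 3.2). The exact interval would look like a full statement of uncertainty when it is not.

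**Working it through.** **Reproducing the plan's figure.** The exact (Clopper-Pearson) interval for 22/26 = 84.6% is 65.1% to 95.6%, which agrees with the stated 65% to 96%. All six rows of the sensitivity table and all four rows of the specificity table also reproduce to rounding.

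**How many are unverified.**
- Not operated: 43 − 32 = 11, and 11/43 = 25.6%.
- Operated without true progression: 32 − 26 = 6.
- True progressions among the 11, at the operated rate: 11 × 26/32 = 8.9, about 9. The total is then 26 + 9 = 35, and 9/35 = 26% lie outside the primary estimate.

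Section 10.0 does not say whether disease progression means true or radiographic progression, or whether a subject may count under both progression and pseudoprogression. Two other readings bracket the share lost:
- 26 true progressions + 17 pseudoprogressions (6 by pathology, 11 by scan) = 43: none lost.
- All 43 true progressions: (43 − 26)/43 = 39.5% without pathological proof.

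**Best/worst-case bounds when 22 of 26 are detected.** Count every unverified progression as missed, then as detected.
- 35 true progressions: 22/35 = 63% to 31/35 = 89%. The exact interval is 45% to 79% at the lower bound and 73% to 97% at the upper.
- All 11 unoperated are true progressions (37): 22/37 = 59% to 33/37 = 89%.

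In the first case the bounds span 89 − 63 = 26 points before any sampling error. The planned interval spans 96 − 65 = 31 points for sampling error alone.

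**Size and direction of bias.** Let r be the probability of surgery for a true progressor with rCBV ≥ 1.75 divided by that for one with rCBV < 1.75. The documents give no value, so r is an assumption. For true sensitivity s:

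observed = s·r / (s·r + 1 − s).

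Inverted for 22 detected and 4 missed among the operated: true = (22/r) / (22/r + 4).

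| r | True sensitivity behind an observed 85% |
|---|---|
| 0.5 | 92% |
| 1 | 85% |
| 1.5 | 79% |
| 2 | 73% |
| 3 | 65% |

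A forward example shows that both directions are possible. Take a true sensitivity of 70%. If 85% of high-rCBV and 50% of low-rCBV progressors are operated on, the observed value is 0.595/(0.595 + 0.150) = 80%. With the rates exchanged it is 0.350/(0.350 + 0.255) = 58%.

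**Does the secondary analysis cover this?** It widens the set but makes no correction, and it depends on true progression confirmed by imaging. Section 8.1 defines pseudoprogression by imaging or pathology, but confirmed true progression by histopathology only. Persistent radiographic progression cannot simply stand in, because it is the state that leads to the surgical evaluation. The plan itself expects 6 of 32 operated patients (19%) not to have true progression on pathology.

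**The case against.** The strongest reply is that nothing in the documents says rCBV guides surgery. The formal trigger is growth in enhancement (Section 8.1), the listed criteria concern operability and clinical interest, and Sections 7.4 and 7.6 describe repeat surgery or biopsy at persistent progression as standard of care for this very distinction. The shortfall is put down to dropout and inoperability. If those are unrelated to rCBV, r = 1 and there is no bias. This stands as far as it goes: a reader might infer that the headline sensitivity is inflated, and the documents do not establish that. The provision for biopsy not thought clinically necessary could even apply to obvious progression with high rCBV, which would push the estimate down. But the documents do not exclude a link either, and the plan has no means of detecting one.

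A reader might also infer that the operated-only rule discards about 40% of expected progressions, with bounds of 22/43 to 39/43 (51% to 91%). That does not follow. Six of those 17 subjects are operated on and have surgical results; pathology did not show true progression. The surgery restriction leaves out 11 of 43. The 40% needs the extreme reading that all 43 are true progressions. The opposite reading, none lost, fits the totals but sits poorly with attributing the 11 to dropout and inoperability.

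Two further replies have weight. The secondary analysis does widen the set, and its wording does not rule out the 1.75 cut-off. And in a descriptive pilot no test or decision rule turns on this estimate.

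**Conclusion.** The concern holds as a risk that the plan leaves unaddressed. On the plan's figures 26% of subjects are unverified by pathology, about 9 of 35 true progressions, with 0% to 40% possible because the planning text is ambiguous. The figure of 9 assumes that the unoperated have the operated group's 26/32 rate of true progression.

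The direction of any bias is unknown. Upward is plausible given the centre's stated confidence in rCBV. If r is 1.5 to 2, an observed 85% overstates the truth by about 6 to 11 points (85% against 79% and 73%). If r = 0.5 it understates it by about 7 (85% against 92%). The exact interval shows none of this, and the secondary analysis lacks both a correction and a defined reference standard. This should be fixed, but in a descriptive pilot it affects how the estimate is read and not whether the trial can proceed.

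**What to change.** Keep the 1.75 cut-off and the operated-only sensitivity. Beside it, at 1.75 and for all subjects with persistent radiographic progression and a ferumoxytol MRI, report:

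1. A Begg-Greenes corrected sensitivity by rCBV class. With n₊ and n₋ the numbers of such subjects at or above and below 1.75, and p₊ and p₋ the proportions of the operated in each class with true progression, sensitivity = n₊p₊ / (n₊p₊ + n₋p₋), with a bootstrap confidence interval.
2. Best/worst-case bounds, with the denominator stated.

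A weighting model with several covariates is not advised. About 11 subjects are unverified, the planning case has 4 verified misses, and the documents describe no recorded accessibility variable.

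Also define in Section 8.1 or 10.0 the imaging reference standard for true progression used in the secondary analysis; state whether progression in the planning text means true or radiographic; record for each case whether rCBV informed the surgery decision; and give the existing pathologist the specimen without the rCBV result.

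The cost is SAP wording, a short extra analysis of scans already scheduled, one recorded item per case and a small change in specimen handling. Sample size and treatment do not change. The corrected interval will probably be wider, and the estimate relies on surgery being independent of disease status within each rCBV class. Dropouts never scanned at progression have no rCBV and stay outside it.
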